11.4.2 Statistical/Analytical Issues

11.4.2.1 Adjustments for Covariates

The primary efficacy endpoint (aerobic exercise performance) and some of the secondary efficacy endpoints were analyzed with an ANCOVA model with fixed factors for ventricular morphology and treatment groups with a covariate of the relevant baseline value.

11.4.2.2 Handling of Dropouts or Missing Data

The following imputation method was used for the primary analysis of the primary outcome:

- Subjects who died or dropped out of the study with unknown vital status were to be assigned a maximal VO_2 of zero at Week 26. No subject met this criterion.
- Subjects who were known to be alive, but who discontinued from the study (and were missing maximal VO_2 at Week 26) were assigned the latest value available.

- Subjects who completed Week 26 but were physically unable to reach maximum effort in cardiopulmonary exercise testing after 2 attempts, were assigned their baseline value (ie, zero change).

Two additional sensitivity analyses to assess the impact of missing data were conducted as follows:

- Subjects with missing maximal VO₂ at Week 26 were assigned a maximal VO₂ of zero.
- Subjects with missing maximal VO₂ at Week 26 were excluded from analysis (ie, observed cases analysis).

An additional imputation method for missing data was included for exercise variables. When the Week 26 value was missing, the mean of non-missing Week 26 values (ignoring treatment group) was imputed.

For VO₂ at VAT, a linear regression model was used to predict Week 26 VO₂ at VAT from Week 26 maximal VO₂. The predicted value from the model was used to impute VO₂ at VAT when maximal VO₂ was available; when maximal VO₂ was also missing, the average from all subjects with non-missing values was imputed.

Missing item scores for rating scales were imputed according to published methodology for the scale. Otherwise, missing data were not estimated for secondary efficacy endpoints.

11.4.2.3 Interim Analyses and Data Monitoring

The PHN DSMB convened at least twice per year to review safety data. In addition, the DSMB was asked to review all data after the first 50 subjects had completed the study.

Formal stopping boundaries were not proposed for the 26-week study. However, the DSMB could have recommended stopping the study for other reasons, such as safety findings from this study and other studies or concerns about study conduct. In addition, premature termination of this study could have occurred due to the impact of results released from other studies, due to failure to enroll, or due to withdrawal of study approval by clinical site IRBs. In addition, the NHLBI retained the right to discontinue the study prior to the inclusion of the intended number of subjects but intended to exercise these rights only for valid scientific or administrative reasons.

After primary outcome data were obtained for approximately half of the originally planned sample size (approximately N=200 subjects), the variance of the primary outcome was estimated using a blinded method with lumped variance. If this estimated variance was higher than the one used for the sample size calculations, then the sample size would have been recalculated and increased correspondingly. Otherwise, the sample size would not change, and the study would proceed as planned. This approach was based on blinded re-estimation of nuisance parameters and did not lead to inflation of type I error. It was consistent with the regulatory guidance for industry in adaptive design of clinical studies.

The estimated variance at the interim analysis did not require an increase in sample size.

11.4.2.4 Multicenter Studies

The study was conducted at 30 sites. Change in maximal VO₂ is summarized by site in [Table 14.2.1.2.5](#) using units of mL/min and in [Table 14.2.2.2.5](#) using units of mL/kg/min. Change in VO₂ at VAT is summarized by site in [Table 14.2.3.2.6](#) using units of mL/min and in [Table 14.2.4.2.6](#) using units of mL/kg/min.

11.4.2.5 Multiple Comparison/Multiplicity

Formal hypothesis testing was performed only for the primary efficacy endpoint. No adjustment for multiple comparisons was made for secondary efficacy endpoints.

11.4.2.6 Use of an "Efficacy Subset" of Subjects

The primary efficacy analysis was performed with the ITT population, which included all randomized subjects and was the primary population for efficacy analyses. Sensitivity analyses were performed for the Per Protocol population ([Table 14.2.1.1.4](#), [Table 14.2.1.2.4](#), [Table 14.2.2.1.4](#), and [Table 14.2.2.2.4](#)), which included all treated subjects who met all entry criteria or, if criteria were not met, were granted a waiver by the Sponsor; subjects with major protocol deviations were excluded.

11.4.2.7 Active-Control Studies Intended to Show Equivalence

[figure not shown]
An active control was not used in this study.

11.4.2.8 Examination of Subgroups

The treatment group difference (udenafil minus placebo) for change in maximal VO₂ from baseline to Week 26 was positive for most subgroups ([Figure 2](#)). Positive differences indicate greater mean improvement from baseline for udenafil than for placebo.

Treatment group differences are also presented in mL/min without imputation by gender ([Table 14.2.1.1.2.1](#)), race ([Table 14.2.1.1.2.2](#)), ethnicity ([Table 14.2.1.1.2.3](#)), ventricular morphology ([Table 14.2.1.1.2.4](#)), age at Fontan surgery ([Table 14.2.1.1.2.5](#)), baseline serum BNP ([Table 14.2.1.1.2.6](#)), percent predicted maximal VO₂ at baseline ([Table 14.2.1.1.2.7](#)), and use of afterload reducing agents ([Table 14.2.1.1.2.8](#)).

Figure 2: Treatment Group Difference in Mean Maximal VO₂ (mL/min) With 95% Confidence Interval for Change Between Week 26 and Baseline Visits in Subpopulations Using Last Observation Carried Forward (ITT Population)

%p=percent predicted; BNP=brain natriuretic peptide; ITT=intent-to-treat; VO₂=minute oxygen consumption; yrs=years
Note: No imputation was performed.

Source: [Figure 14.2.1.1.6](#)

[figure not shown]
Program: [f_forestplot](#)

The treatment group difference (udenafil minus placebo) for change in maximal VO₂ (mL/kg/min) from baseline to Week 26 was positive for most subgroups ([Figure 3](#)). Positive differences indicate less mean deterioration from baseline for udenafil than for placebo.

Treatment group differences are also presented in mL/kg/min without imputation by gender ([Table 14.2.2.1.2.1](#)), race ([Table 14.2.2.1.2.2](#)), ethnicity ([Table 14.2.2.1.2.3](#)), ventricular morphology ([Table 14.2.2.1.2.4](#)), age at Fontan surgery ([Table 14.2.2.1.2.5](#)), baseline serum

BNP ([Table 14.2.2.1.2.6](#)), percent predicted maximal VO_2 at baseline ([Table 14.2.2.1.2.7](#)), and use of afterload reducing agents ([Table 14.2.2.1.2.8](#)).

Figure 3: Treatment Group Difference in Mean Maximal VO_2 (mL/kg/min) With 95% Confidence Interval for Change Between Week 26 and Baseline Visits in Subpopulations Using Last Observation Carried Forward (ITT Population)

%p=percent predicted; BNP=brain natriuretic peptide; ITT=intent-to-treat; VO_2 =minute oxygen consumption; yrs=years
Note: No imputation was performed.

[figure not shown]
Source: [Figure 14.2.1.1.7](#)

Program: [f_forestplot](#)

The treatment group difference (udenafil minus placebo) for change in VO_2 at VAT (mL/min) from baseline to Week 26 was positive for all subgroups ([Figure 4](#)). Positive differences indicate greater mean improvement from baseline for udenafil than for placebo.

Treatment group differences are also presented in mL/min without imputation by gender (Table 14.2.3.1.2.1), race (Table 14.2.3.1.2.2), ethnicity (Table 14.2.3.1.2.3), ventricular morphology (Table 14.2.3.1.2.4), age at Fontan surgery (Table 14.2.3.1.2.5), baseline serum BNP (Table 14.2.3.1.2.6), percent of predicted maximal VO₂ at baseline (Table 14.2.3.1.2.7), and use of afterload reducing agents (Table 14.2.3.1.2.8).

Figure 4: Treatment Group Difference in Mean VO₂ (mL/min) at VAT With 95% Confidence Interval for Change Between Week 26 and Baseline Visits in Subpopulations Using Last Observation Carried Forward (ITT Population)

%p=percent predicted; BNP=brain natriuretic peptide; ITT=intent-to-treat; VAT=ventilatory anaerobic threshold;
VO₂=minute oxygen consumption; yrs=years

[figure not shown]
Note: No imputation was performed. Subjects with unknown race and ethnicity were excluded from the respective analysis.

Source: [Figure 14.2.2.1.6](#)

Program: [f_forestplot](#)

The treatment group difference (udenafil minus placebo) for change in VO₂ at VAT (mL/kg/min) from baseline to Week 26 was positive for all subgroups (Figure 5). Positive differences indicate less mean deterioration from baseline for udenafil than for placebo.

Figure 5: Treatment Group Difference in Mean VO₂ (mL/kg/min) at VAT With 95% Confidence Interval for Change Between Week 26 and Baseline Visits in Subpopulations Using Last Observation Carried Forward (ITT Population)

%p=percent predicted; BNP=brain natriuretic peptide; ITT=intent-to-treat; VAT=ventilatory anaerobic threshold;
VO₂=minute oxygen consumption; yrs=years

Note: No imputation was performed. Subjects with unknown race and ethnicity were excluded from the respective analysis.

Source: [Figure 14.2.2.1.7](#)

Program: [f_forestplot](#)

11.4.3 Tabulation of Individual Response Data

Tabulations of individual response data are found in [Appendix 16.2](#).

11.4.4 Drug Dose, Drug Concentration, and Relationships to Response

Drug dose and drug concentration relationships to response were not assessed.

11.4.5 Drug-Drug and Drug-Disease Interactions

Drug-drug and drug-disease interactions were not assessed.

11.4.6 By-Subject Displays

There were no by-subject displays of individual response to study drug except as provided in the data listings ([Appendix 16.2](#)).

11.4.7 Efficacy Conclusions

Key Efficacy Findings

The primary aim of this study was to evaluate the effect of 26 weeks of treatment with udenafil on exercise capacity in adolescents with Fontan physiology. The protocol-specified primary exercise outcome was change in maximal VO_2 and secondary exercise outcomes included change in VO_2 at VAT, change in ventilatory efficiency at VAT, and work rate at VAT. All exercise measures demonstrated a favorable outcome for udenafil relative to placebo.

For maximal VO_2 , the udenafil group had a mean increase from baseline to Week 26 compared to a mean decrease in the placebo group (44.40 mL/min versus -3.65 mL/min; $p=0.071$). When standardized by each subject's body weight, the least squares mean treatment group difference was 0.64 mL/kg/min ($p=0.092$).

The following secondary efficacy endpoints measured at VAT also indicated greater exercise capacity in the udenafil group than the placebo group at Week 26:

- VO₂ at VAT: Mean increase (improvement) for udenafil as compared to a mean decrease in the placebo group (29.65 mL/min versus -8.01 mL/min; p=0.023). When standardized by each subject's body weight, the least squares mean treatment group difference was 0.78 mL/kg/min (p=0.012).
- VE/VCO₂ at VAT: Greater mean decrease (improvement) for udenafil as compared to placebo (-0.76 versus -0.05; p=0.011).
- Work rate at VAT: Greater mean increase (improvement) for udenafil as compared to placebo (3.46 watts versus 0.31 watts; p=0.029).

An additional efficacy aim evaluated the effect of 26 weeks of treatment with udenafil on the performance of a single ventricle. The primary measure of ventricular performance was change in MPI, which indicated improvement with udenafil versus placebo (-0.02 vs 0.01; p=0.024).

Relative Utility of Maximal VO₂ Versus VO₂ at VAT

The protocol-specified primary endpoint of maximal VO₂ measures overall aerobic capacity and has been shown to be useful as a predictor of cardiac death and hospitalization for heart failure, both in congenital and acquired heart disease. Given the relative ease of obtaining this measure and its utility as a surrogate outcome, maximal VO₂ has been chosen as an endpoint in multiple observational studies and clinical trials. In view of the above, and to be consistent with generally accepted understanding in the pediatric cardiology community, maximal VO₂ was chosen as the primary endpoint for the FUEL trial. An alternative exercise measure, VO₂ at VAT, was also considered during the initial study design, but was designated as a secondary endpoint for 2 reasons: 1) There were more limited relevant data from prior studies to allow for a robust power calculation, and 2) VO₂ at VAT is more difficult to measure precisely, which could lead to data loss and impact statistical power in this rare pediatric disease. The concern about data loss was confirmed in the FUEL trial in which 21% of participants did not have paired data VO₂ at VAT ([Table 14.2.3.1.2](#)) versus 5% for maximal VO₂ ([Table 14.2.1.1.2](#)).

Despite its utility in most forms of heart disease, recent publications suggest that maximal VO₂ may not be an ideal efficacy measure for interventions in Fontan physiology, particularly for therapies that would improve exercise performance by modification of the PVR. During

exercise, there is a substantial increase in metabolic demand for oxygen delivery and, therefore, cardiac output. In the absence of a sub-pulmonary pump, preload is maintained by the pressure gradient across the pulmonary vascular bed; the difference between CVP and atrial pressure. As exercise intensity increases, CVP must rise to allow for increased transpulmonary blood flow (Qp). Udenafil may modulate this relationship by lowering PVR and therefore allowing for a lower CVP for any given amount of Qp. However, as exercise intensity increases, modification of PVR alone may not be sufficient to allow for the needed increase in cardiac output. Even with optimal pulmonary vasodilation, an increase in CVP is required to provide adequate Qp to keep up with metabolic demand. At the highest levels of exertion, one begins to exceed the physiologic limit of maximal CVP. This physiologic limit, or ceiling, is that point at which exercise is limited by an inability to raise CVP any further.

In a person with a structurally normal heart, there is no physiologic ceiling during exercise related to venous pressure. CVP, which starts at 5 to 7 mmHg, is unchanged during exercise as pulmonary blood flow is driven by the sub-pulmonary right ventricle. In a person who has undergone Fontan palliation and does not have a sub-pulmonary ventricle, CVP starts out much higher (12 to 15 mmHg) and then increases dramatically with exercise. This high pressure cannot be sustained beyond the physiologic ceiling and results in limited ability to maintain ventricular preload and increase cardiac output at higher levels of aerobic exertion. Thus, while pulmonary vasodilators may improve exercise capacity at moderate levels of activity, there is a physiologic limit to their ability to impact performance at levels of exertion approaching the physiologic ceiling. Studies published since the inception of the FUEL trial highlight these unique physiological limitations in the Fontan circulation and point away from the selection of maximal VO₂ as an endpoint for this specific type of congenital heart disease ([Goldberg 2021](#); [Navaratnam 2016](#)).

As a consequence of the physiologic limitations associated with Fontan palliation, therapies designed to improve aerobic capacity by decreasing PVR will have their greatest impact at lower levels of aerobic activity and thus lower levels of CVP. VO₂ at VAT is a measure of submaximal exercise that represents the physiologic point at which the metabolic demands of the exercising muscles begin to outstrip the ability of the cardiovascular system to deliver adequate amounts of oxygen to meet those demands. While VO₂ at VAT is more technically difficult to measure than peak VO₂, it has the same association with important morbidities and mortality as maximal VO₂ ([Gitt 2002](#); [Malhotra 2016](#); [Tsai 2018](#)). Given the unique features of the Fontan circulation, VO₂ at VAT, despite the challenges associated with data acquisition, is more robust as a surrogate endpoint for this population than maximal VO₂. Given the lack of understanding in the field of this unique physiology at the time of conception of the FUEL trial, the power analysis for maximal VO₂ was predicated on the

impact of alterations in PVR on exercise capacity for those with other forms of heart disease. Although udenafil may have some effect on maximal VO₂, this effect is blunted by the physiologic ceiling of CVP. The expanded understanding of Fontan physiology in recent years has taught that the assumptions informing the selection of maximal VO₂ as the primary endpoint were inaccurate, and that VO₂ at VAT is a more useful endpoint for this unique cohort of patients.

Overall Efficacy Conclusions

In summary, treatment with udenafil for 26 weeks resulted in improvements in exercise capacity, as well as an improvement in the performance of the single ventricle. Although the primary endpoint did not reach statistical significance, new knowledge of the limits of the Fontan circulation explains why this endpoint is an imperfect choice for this circulation. Even with the limitations associated with maximal VO₂, this endpoint showed a clear trend toward improvement that, coupled with the improvement at the anaerobic threshold, speaks to the efficacy of udenafil to improve exercise capacity in this population. Based on the superior exercise capacity and ventricular performance for udenafil as compared to placebo at Week 26, this study achieved its primary clinical objective for a population with no pharmacotherapeutic options.

12 Safety Evaluation

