9.7 Statistical Methods Planned in the Protocol and Determination of Sample Size

9.7.1 Statistical and Analytical Plans

The statistical methods described below are summarized from the final Statistical Analysis Plan (SAP), dated 23 June 2016. Changes from the planned analyses in the protocol that were specified in the final SAP are described in [Section 9.8.2](#).

Formal hypothesis testing was performed only for the primary efficacy endpoint. All statistical tests were at the 0.05 alpha level, 2-tailed, unless stated otherwise. Descriptive statistics for categorical endpoints included the number and percent of subjects in each treatment group and category. Quantitative endpoints were summarized for each treatment group with the mean, median, standard deviation, minimum value, and maximum value. Individual subject data were presented in data listings that included normal reference ranges when appropriate.

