The incidence of TEAEs of Grade ≥ 3 , serious TEAEs, drug-related serious TEAEs, and TEAEs resulting in temporary or permanent discontinuation of study drug was similar between treatment groups. No subject died during the study. No individual serious TEAE was reported by > 2 subjects in either treatment group. Hospitalization was reported for 23 subjects (14 udenafil, 9 placebo) during the study.

There were no clinically important treatment group differences for clinical laboratory findings and vital signs. Overall, udenafil was safe and well tolerated in this study.

In summary, this study achieved its primary clinical objectives by demonstrating that udenafil administered orally at 87.5 mg BID for 26 weeks led to improved exercise capacity as compared to placebo in adolescents with Fontan physiology. In addition, myocardial performance was improved in the group treated with udenafil.

14 Tables, Figures and Graphs Referred to but not Included in the Text

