6.4.5 Adjustments for Multiple Comparisons

Formal hypothesis testing will be performed only for the primary efficacy endpoint. Thus, no adjustment for multiple comparisons will be necessary.

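### Sections 11.4.7 and 13 of the study report say the primary clinical objective was achieved, but the only formally tested endpoint was not significant (p=0.092 in the protocol-specified unit)

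*Protocol*

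**What the plan says.** The document supplied as the Protocol is a clinical study report; it is called the report here.

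- **What was to be tested.** SAP 6.4.5: "Formal hypothesis testing will be performed only for the primary efficacy endpoint. Thus, no adjustment for multiple comparisons will be necessary". Report Section 9.7.1 repeats the rule: "Formal hypothesis testing was performed only for the primary efficacy endpoint". Tests are two-sided at 0.05 (SAP 6.0; report 9.7.1). The primary variable is change in maximal VO2 from baseline to Week 26 (report 9.5.3; SAP 6.4.1).
- **Secondary endpoints.** SAP 6.4.2 prespecifies VO2, VE/VCO2 and work rate at VAT, and MPI, as secondary. Report 11.4.2.5: "No adjustment for multiple comparisons was made for secondary efficacy endpoints".
- **Unit.** Section 9.8.2.3, on changes after blind break, names mL/kg/min as the protocol-specified unit and records mL/min as added. The SAP sample size (3.0) is also in mL/kg/min.
- **Result.** Table 13 gives 0.64 mL/kg/min (p=0.092) and 41.04 mL/min (p=0.071).
- **Conclusions.** The summary in Section 11.4.7 opens with "Although the primary endpoint did not reach statistical significance". It goes on to say "this endpoint showed a clear trend toward improvement" and, "Based on the superior exercise capacity and ventricular performance for udenafil as compared to placebo at Week 26", that "this study achieved its primary clinical objective for a population with no pharmacotherapeutic options". The summary closing Section 13 says "this study achieved its primary clinical objectives by demonstrating that udenafil" improved exercise capacity relative to placebo.

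**The concern.** A trial with one formal test has one confirmatory answer, and here that answer is negative. A claim that the objective was achieved, and in Section 13 that benefit was demonstrated, is a confirmatory claim. It has to come from the maximal VO2 test, because no other endpoint carries controlled error.

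These are the report's closing efficacy statements and the ones most likely to be carried forward. A reader of the last paragraph of Section 13 would take away a positive trial. The plan supports a missed primary endpoint with nominal secondary signals.

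Section 11.4.1 has a related problem. It gives p=0.071 alone as the result of the primary analysis, although the protocol-specified unit gives 0.092.

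**Working it through.** **Inputs.** Table 13 gives the least squares mean differences and standard errors: 0.64 (0.377) mL/kg/min and 41.04 (22.709) mL/min, with 200 subjects per group. The model in SAP 6.4.1 has an intercept, morphology, treatment and baseline, so df = 400 - 4 = 396 and the two-sided 5% critical value is 1.966.

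**Step 1: reproduce the reported p-values** (t = estimate / SE).

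- mL/kg/min: 0.64 / 0.377 = 1.698, p = 0.090. Rounding of the inputs (estimate 0.635 to 0.645, SE 0.3765 to 0.3775) allows 0.0875 to 0.0933, which contains the reported 0.092.
- mL/min: 41.04 / 22.709 = 1.807, p = 0.0715, against the reported 0.071.

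**Step 2: intervals** (estimate ± 1.966 × SE).

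- mL/kg/min: 0.64 ± 0.741, or -0.10 to 1.38. Rounding moves the lower limit between -0.107 and -0.095 and the upper between 1.375 and 1.387.
- mL/min: 41.04 ± 44.65, or about -3.6 to 85.7.

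Both include zero, so the test fails at 0.05 in either unit. For scale, 0.64 is 23% of the 2.8 mL/kg/min in the sample size calculation (0.64 / 2.8). The verdict does not depend on that.

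**Step 3: all reported maximal VO2 p-values** (Section 11.4.1.2).

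| Analysis | mL/kg/min | mL/min (unit added after blind break) |
|---|---|---|
| ITT, LOCF (primary) | 0.092 | 0.071 |
| Observed cases (SAP 6.4.3) | 0.089 | 0.062 |
| Zero imputation (SAP 6.4.3) | 0.422 | 0.045 |
| Per Protocol, LOCF (SAP 6.4.1) | 0.188 | 0.161 |
| Ranked, LOCF (SAP 6.4.1) | 0.069 | 0.026 |
| Mean imputation (added after blind break) | 0.083 | 0.032 |
| Log scale, LOCF | 0.072 | 0.070 |
| Log scale, observed cases | 0.073 | 0.061 |
| Log scale, mean imputation | 0.075 | 0.033 |
| Log scale, Per Protocol | 0.202 | 0.176 |

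In mL/kg/min, none of ten is below 0.05. In mL/min, four of ten are, and none of those four is the primary analysis.

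**Step 4: what the success wording rests on.** Without imputation, as SAP 6.4.3 plans for secondary endpoints, the p-values are: VO2 at VAT 0.009 (mL/kg/min) and 0.012 (mL/min), VE/VCO2 at VAT 0.014, work rate at VAT 0.021, and MPI 0.024. All are nominally below 0.05. The SAP defines no family and no adjustment method, so no adjusted value can be given.

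**Step 5: a smaller wording point.** Section 11.4.1.3 describes ranked VO2 at VAT results of 0.075 (mL/min) and 0.152 (mL/kg/min) as similar to results that are all 0.032 or less. SAP 6.4.1 plans ranked analyses for maximal VO2 only.

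**The case against.** The best defence separates objective from endpoint. Section 8 states the primary objective broadly, as evaluating the effect on exercise capacity, and SAP 6.4.2 lists the VAT measures under exercise capacity. Section 11.4.7 also argues at length that maximal VO2 suits the Fontan circulation poorly. This has some force for 11.4.7, where the miss is stated in the same paragraph. It does not rescue the wording. An objective to evaluate is met whatever the result, whereas these passages claim benefit, and Section 13 claims it was demonstrated. Section 11.4.1 itself ties the aim to maximal VO2 as the primary outcome. The physiological argument may be sound, but it cannot change which endpoint was formally tested.

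Other points on that side stand:

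- A reader might infer that the report hides the miss. It does not. Section 11.4.7 says so outright, and Section 13 names maximal VO2 as the protocol-specified primary outcome and prints both p-values. What Section 13 lacks is the sentence drawing the conclusion.
- The VAT and MPI endpoints are not post hoc. They are prespecified secondary endpoints with a planned ANCOVA, so calling them exploratory would go beyond the documents.
- The ranked mL/min result of 0.026 applies a planned method in a unit that was not planned. It should not be presented as a planned result, nor be singled out from the other sensitivity analyses.
- Section 11.4.1 does say that mL/min is additional, and 11.4.1.1 gives 0.092 soon after. Section 11.4.1.2 also uses the similarity phrase loosely (0.069 beside 0.422). Steps 4 and 5 of the fix are therefore secondary.

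**Conclusion.** The concern holds as a conflict between the report's conclusions and its own plan. The one formal test missed at two-sided 0.05: 0.64 mL/kg/min, p=0.092, 95% CI about -0.10 to 1.38. It also missed in the added unit: 41.04 mL/min, p=0.071. The statements that the objective was achieved, and that improvement was demonstrated, are not supported and need correcting.

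The intervals assume 396 degrees of freedom and use rounded table values; exact limits should come from the model output. The verdict does not depend on the choice of unit.

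Two stronger readings are not supported. The data do not show that udenafil has no effect: the estimate favours udenafil and the interval allows a benefit. Nor can it be said that the secondary findings would vanish under adjustment, since no adjustment was defined. No defect in the SAP is claimed on this point.

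**What to change.** Change the report text only.

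1. **Sections 11.4.7 and 13.** Replace the claims that the primary clinical objective(s) were achieved, and the claim of demonstration in Section 13, with a statement that the primary endpoint was not met. Give 0.64 mL/kg/min, p=0.092, first, with its 95% CI from the model output. Then give 41.04 mL/min, p=0.071, marked as a unit added after blind break.
2. **Sensitivity results.** If any are quoted in the conclusions, give all the SAP-planned ones reported in mL/kg/min together: Per Protocol 0.188, ranked 0.069, observed cases 0.089, zero imputation 0.422. Mark every mL/min result, including ranked 0.026, as being in the added unit.
3. **Wording of strength.** In 11.4.7, describe maximal VO2 as showing a non-significant difference in favour of udenafil, not a clear trend. Replace the claim of superiority with wording that calls the VAT and MPI results nominal, unadjusted secondary findings. Bring the statements on improved exercise capacity (11.4.7) and improved myocardial performance (13) into line.
4. **Section 11.4.1.** Report p=0.092 in mL/kg/min as the primary analysis, with p=0.071 as the added unit.
5. **Section 11.4.1.3 (minor).** Do not describe the ranked VO2 at VAT results as similar to the others, and note that the SAP plans ranks for maximal VO2 only.

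Do not amend the SAP or add a testing sequence after unblinding. The cost is wording in four sections and one confidence interval from existing output, with no new data. The price is a less favourable headline.
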